9.1.4.5 Patient Reported Outcome

The impact of the disease on patient's Quality of Life will be measured at baseline and during the treatment using the St George Respiratory Questionnaire and the EuroQol questionnaire.

9.2 SAFETY ENDPOINTS

The same safety assessment will be applied across all arms. Adverse events will be collected at each visit from the signing of the informed consent to the end of the follow-up period. The investigator will ask the patient how he/she has felt since the last study visit/phone call. The study specific and general safety monitoring are detailed in [Section 10.4.1](#). To ensure the continuing safety of patients in this study, an independent DMC will be responsible for reviewing the safety data on a periodic basis throughout the course of the study as outlined in [Section 6.3](#).

9.2.1 Adverse events

Refer to [Section 10.4](#) to [Section 10.7](#) for details.

9.2.2 Physical examination

A complete physical examination will be performed at each site-visit as per study flowchart (Section 1.2) and description of study procedures in [Section 10](#).

Specific attention will be paid to skin, nasal cavities, eyes, ears, respiratory, cardiovascular, gastrointestinal, neurological, lymphatic, and musculoskeletal systems. For the dermatological exam, it is recommended that the patient wears only undergarments. [REDACTED]

[REDACTED] Nail beds (periungual areas) should be examined for "splinter lesions" and digital tuft for tuft purpura or ischemia. For neurological examination, the Investigator should focus on CNS signs and refer to a neurologist if further assessments are deemed necessary.

Clinically significant abnormalities should be reported in the patient e-CRF as medical history, if observed at the screening visit (Visit1) or as an AE if observed during subsequent visits.

9.2.3 Laboratory safety variables

The clinical laboratory data consist of blood analysis (including hematology, clinical chemistry) and urinalysis. Clinical laboratory values will be analyzed after conversion into standard international units. International units will be used in all listings and tables.

The clinical laboratory tests will be conducted by an accredited (college of American Pathologists or equivalent) central laboratory with national and regional clinical licenses as required for diagnostic testing and must provide evidence of participation in proficiency testing, as appropriate. After reviewing the laboratory report and evaluating any results that are outside the normal range, the Investigator must sign and date the laboratory report. Abnormal laboratory values that are considered to be clinically significant by the Investigator must be repeated as soon as possible after receiving the laboratory report to rule out laboratory error. Persistent abnormal laboratory values should be repeated until they return to normal or until an etiology of a persistent abnormality is determined.

Samples will be taken at the study site before administration of the IMPs. The following parameters will be measured as per study flowchart ([Section 1.2](#)) and description of study procedures in [Section 10](#).

- Hematology
Hemoglobin, hematocrit, red blood cell count, erythrocyte sedimentation rate (ESR), white blood cell count with differential and platelet count.
- Serum chemistry

Fasting glucose, blood urea nitrogen, creatinine, sodium, potassium, chloride, bicarbonate, calcium, phosphorous, total protein, albumin, total bilirubin, alkaline phosphatase, ALT, AST, CPK, high-sensitivity C-reactive protein (hsCRP).

- Urine analysis including specific gravity, pH, glucose, ketones, blood, protein, nitrate, leukocyte esterase, urobilinogen and bilirubin (by dipstick). If any parameter on the dipstick is abnormal, a urine sample should be sent to the central laboratory for testing. If positive for proteins, microscopic analysis is performed by central laboratory.

For women of childbearing potential, a serum pregnancy test (β -human chorionic gonadotrophin) and urine pregnancy tests will be performed as per study flow chart in [Section 1.2](#). From Visit 4, the site will dispense urine pregnancy kits to the patients who will perform the test at home on a monthly basis. If any interim urine pregnancy test performed by the patient is positive, the patient should immediately report to the investigator for appropriate follow-up and pregnancy reporting as appropriate.

- Clinical laboratory testing at Visit 1 adds hepatitis screen (hepatitis B surface antigen, hepatitis B surface antibody, hepatitis B core antibody and hepatitis C antibodies) and tuberculosis screen (Quantiferon®- TB gold evaluation)

- 

Decision trees for the management of some laboratory abnormalities are provided in [APPENDIX F](#).

9.2.4 Vital signs

Vital signs include blood pressure (mmHg), heart rate (beats per minute), body weight (kg) and height (cm).

Blood pressure will be measured at each site study visit in sitting position. Both systolic and diastolic BP should be recorded. BP should be checked after 5 minutes of resting in sitting position.

Weight should be taken with the patient wearing undergarments or very light clothing and no shoes and with an empty bladder. The same scale should be used throughout the study.

Height will be measured at screening (Visit 1) only.

Body mass index (BMI) will be calculated automatically at each visit.

9.2.5 Electrocardiogram variables

A standard 12-lead ECG will be performed at each on site visit as per study flowchart ([Section 1.2](#)) and description of study procedures in [Section 10](#). ECG data will be assessed by the Investigator based on the automatic device reading.

At the post randomization visits, ECGs will be performed prior to investigational product administration. All ECGs will be performed with the subject in a reclined position. ECG parameters include: Heart rate, QRS duration, PR interval, QT interval, ST deviation, T-wave and Uwave morphology.

9.2.6 Hypersensitivity/Allergic or anaphylactic reactions

Assessment, categorization and treatment of systemic allergic reactions, if any, or of anaphylactic reactions as consensually defined ([26](#)) ([25](#)) will be specifically performed as detailed in [Section 10.6.3.1](#) and following [APPENDIX D](#), as appropriate.

Local injection reactions will be assessed to determine if of allergic origin or not following details provided in [Section 10.6.2](#) and [Section 10.6.3.2](#) (see also [APPENDIX D](#) and [APPENDIX E](#)).

9.3 OTHER ENDPOINTS

9.3.1 Pharmacokinetics

9.3.1.1 Sampling time

Samples for PK analysis will be collected at pre-dose (within 2 hours before each dose administration) during Visits 2, 4, 6, 7, 8 and 9.

Pharmacokinetics samples during Visit 10 will be collected in the morning.

An additional sample should be taken in a sub-group (at least 30 patients by cohort) between 5 and 10 days after last dose (i.e. after Visit 9). The possibility to perform this additional sample will be discussed between Investigator and patient on a case by case basis.

Anti-SAR156597 antibodies (ADA) samples will be collected at approximately the same times as the PK samples.

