The IMP is administered every 7 days +/- 2 days from initial IMP administration. This is permitted per protocol to accommodate special circumstances, eg. laboratory results pending, ongoing AE, patient scheduling difficulty.

If IMP administration is missed or temporarily discontinued, the initial schedule of injections should be resumed. This does not apply to permanent treatment discontinuation.

On days when the patient has a study visit, the IMP will be administered by the Investigator or delegate after clinic procedures and blood collection.

For doses not administered at the study site, the IMP will be administered by qualified site personnel and /or healthcare professionals (e.g. visiting nurse service).

Patients should be monitored by site personnel/visiting nurse for at least 30 minutes after each administration for potential signs and symptoms that may suggest a hypersensitivity reaction.

[For Czech Republic only per local requirement: Patients should be monitored at the study site by site personnel for a minimum of 2 hours after the first administration of IMP and for a minimum of 1 hour after the next 5 administrations for potential signs and symptoms that may suggest a hypersensitivity reaction. For the subsequent IMP administrations, patients should be monitored by site personnel/visiting nurse for at least 30 minutes after each administration.]

For doses not given at study site, a booklet will be provided to the patient to record information related to the injections; this booklet will be completed by the visiting nurse after each injection and will be kept as source data in the patient's study file. Patients will be instructed to bring the booklet back at the subsequent site visit for Investigator's review.

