10.3.1 Temporary treatment discontinuation with investigational medicinal product(s)

Temporary treatment discontinuation may be considered by the Investigator because of any suspected AEs. Re-initiation of treatment with the IMP will be done under close and appropriate clinical/and or laboratory monitoring once the Investigator will have considered according to his/her best medical judgment that it is safe to do so (refer to [Section 7.1](#) and [7.2](#)).

[REDACTED]

For all temporary treatment discontinuations, duration and number of undelivered doses should be recorded by the Investigator in the appropriate pages of the e-CRF.

A discontinuation of IMP that is greater than 30 days will be considered permanent and relevant e-CRF sections should be populated.

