#### **2.1.5 Pharmacokinetic variables**

All measurements (scheduled or unscheduled) will be assigned to analysis windows defined in [Table 7](#), in order to provide an assessment of the PK parameter at each time point planned to be collected as per protocol.

Samples for PK analysis are planned to be collected at pre-dose (within 2 hours before each dose administration) during Visits 2 (Day 1), 4 (Week 4), 6 (Week 12), 7 (Week 24), 8 (Week 36) and 9/EOT (Week 52). Pharmacokinetics samples during Visit 10 will be collected in the morning. An additional sample should be taken in a subgroup (at least 30 patients by cohort) between 5 and 10 days after last dose (i.e. after Visit 9). The possibility to perform this additional sample will be discussed between Investigator and patient on a case by case basis.

Pharmacokinetic variable is the SAR156597 concentration at each time point using the time windows defined in Table 8. Depending on the timing of the sample versus the previous injection,  $C_{\text{trough}}$ ,  $C_{\text{trough,av}}$ ,  $C_{\text{max}}$  and  $C_{\text{Follow-Up}}$  will be defined as follows:

- $C_{\text{max}}$ : SAR156597 concentration sample taken 5 to 10 days after last injection (week 52);
- $C_{\text{trough}}$ : SAR156597 concentration sample within 2h before each administration (day 1, week 4, week 12, week 24, week 36 and week 52);
- $C_{\text{trough,av,ss}}$ : SAR156597 average trough concentrations (“ $C_{\text{trough,av,ss}}$ ”) will be calculated for each patient as the mean of “ $C_{\text{troughs}}$ ” considered at steady state (ss). The occurrence of steady state will be assessed graphically, by plotting “ $C_{\text{trough}}$ ” throughout the study visits over all patients.
- $C_{\text{Follow-up}}$ : SAR156597 concentration sample taken in week 64, 14 weeks after last injection.

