**Table 7 - Analysis windows definition for PK and ADA**

Time point	Targeted study day	Analysis window (in study days)
Week 4	29	27 to 31
Week 12	85	83 to 87
Week 24	169	167 to 171
Week 36	253	251 to 255
Week 52	365	363 to 367
Optional: Week 52+ 5 to 10 days	370	370 to 375
Week 64	449	447 to 451

PK concentrations will be analyzed following time windows as defined below in [Table 8](#). If the date of the previous injection is unknown, the SAR156597 concentration will not be considered for the analysis.

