**Table 8 - Time windows for PK variables definition**

PK variables	Time
C max	W52 + 5 to 10 days
C trough	-2h (day 1, Weeks 12,24,36,52)
C follow-up	Week 64

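### The SAP defines troughs by the injection that follows and never by time since the last active injection, so samples after a missed active dose enter the steady-state trough average.

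*Protocol*

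**What the plan says.** Protocol 9.3.1.1 is a collection instruction for Visits 2, 4, 6, 7, 8 and 9: "Samples for PK analysis will be collected at pre-dose (within 2 hours before each dose administration". It defines no PK variable.

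The definitions are in the SAP. Section 2.1.5 says the variables are assigned "Depending on the timing of the sample versus the previous injection", but for C_trough it then gives only "SAR156597 concentration sample within 2h before each administration (day 1, week 4, week 12, week 24, week 36 and week 52". Table 8 repeats the two-hour limit with a shorter list of visits: "2h (day 1, Weeks 12,24,36,52". Table 7 allocates samples by study day, target ±2 days, without regard to dosing history. The sentence below it is the one exclusion tied to dosing: "If the date of the previous injection is unknown, the SAR156597 concentration will not be considered for the analysis".

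C_trough,av,ss "will be calculated for each patient as the mean of" the troughs considered to be at steady state, and steady state is judged from a plot over all patients. The PK population (SAP 2.3.3) requires one post-dose sample and sets no compliance condition.

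On dosing, every arm is injected weekly and the q2w arm alternates active drug and placebo (Protocol 8.1). Missed doses are not made up: "If IMP administration is missed or temporarily discontinued, the initial schedule of injections should be resumed".

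**The concern.** A trough is fixed by how long ago active drug was last given. The SAP ties it to the injection about to be given, and looks back only to ask whether the date of the previous injection is known. The word active does not appear.

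In the qw arm, a sample taken after a missed dose passes, because the date of the injection before it is known. In the q2w arm a placebo injection can satisfy the check, so a patient who missed active drug still qualifies. Conversely, an unknown placebo date would remove a sample whose active-dose date is on record, although this should be rare because injections are given and recorded by professionals.

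At stake is the trough summary, which serves a secondary objective (SAP 1.2.2), and any later use of C_trough,av,ss. A suspected adverse event is a permitted reason for interrupting treatment (Protocol 10.3.1), so some low values labelled as steady-state troughs would reflect interrupted dosing and not drug disposition. The distortion also differs between the arms being described.

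**Working it through.** The plan states no figure on this point, so there is none to reproduce. The check has two parts.

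**1. Which injection precedes each trough sample?** Post-baseline trough visits are Weeks 4, 12, 24, 36 and 52. With weekly injections, the previous ones fall in Weeks 3, 11, 23, 35 and 51.

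- If q2w starts with active drug on Day 1, active injections fall in even weeks and every previous injection is placebo.
- If it starts with placebo, every previous injection is active and the samples are taken 7 days after active drug.

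The documents say only that the injections alternate. Two labels point to active first. An even-week pre-dose sample is a q2w trough only if active falls in even weeks. SAP 2.1.5 also takes C_max 5 to 10 days after the Week 52 injection, which is near a peak (tmax 4 to 7 days, Protocol 4.1) only if that injection is active.

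With active first, a q2w patient who misses the active injection two weeks before a visit but receives the placebo one week before it is sampled 28 days after active drug. In qw, one missed dose gives 14 days instead of 7.

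**2. How far off is such a sample?** Inputs from the documents: half-life 11 to 15 days (Protocol 4.2.2) and tmax 4 to 7 days (Protocol 4.1). Assumed: one compartment, first-order absorption, linear kinetics.

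- ke = ln 2 / half-life. ka solves tmax = ln(ka/ke)/(ka − ke).
- The contribution of one dose at time t is proportional to g(t) = exp(−ke·t) − exp(−ka·t).
- Steady-state trough with active interval τ: C = Σ g(kτ), k = 1, 2, 3, …
- Trough without the last active dose: C − g(τ). Ratio R = 1 − g(τ)/C.

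Example, q2w, half-life 11 days, tmax 4 days: ke = 0.0630 and ka = 0.644 per day; g(14) = 0.414; C = 0.706; R = 1 − 0.414/0.706 = 0.414.

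| Half-life, tmax (days) | R, q2w (τ = 14) | R, qw (τ = 7) |
|---|---|---|
| 11, 4 | 0.414 | 0.647 |
| 11, 7 | 0.427 | 0.697 |
| 15, 4 | 0.524 | 0.725 |
| 15, 7 | 0.529 | 0.752 |

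**Effect on the patient's average.** Protocol 4.1 reports steady state on Day 43 with weekly dosing, so I take four steady-state troughs (Weeks 12, 24, 36, 52). With one affected, C_trough,av,ss falls by (1 − R)/4:

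- q2w: (1 − 0.529)/4 = 11.8% to (1 − 0.414)/4 = 14.7%
- qw: (1 − 0.752)/4 = 6.2% to (1 − 0.647)/4 = 8.8%

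**Effect on an arm mean.** This needs a missed-dose rate, which the documents do not give. If 5–10% of q2w patients missed the relevant dose (assumption), the arm mean at that visit falls by 0.05 × 0.471 = 2.4% to 0.10 × 0.586 = 5.9%.

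**If placebo came first.** The same model puts the 7-day sample at 1.30 to 1.54 times the 14-day trough, so it would not be a trough.

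**The case against.** The strongest reply is that the SAP does intend to judge PK samples on timing. It says the variables depend on timing against the previous injection, and it drops samples for which that interval cannot be computed. SAP 2.4.7, by contrast, takes ADA samples regardless of timing in relation to injections. On this reading only the numeric interval and the word active are missing. That is a fair account of the intention, but an analyst following the text has no interval to apply, so the sample stays in.

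Second, a low concentration after a missed dose is that patient's true exposure, and removing it from an exposure-response plot would condition on adherence. This stands, and the fix allows for it. It does not justify calling the value a steady-state trough.

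Third, the consequences are modest. The summaries are descriptive. The correlation of C_trough,av,ss is with baseline biomarkers and depends on study results (SAP 2.4.8), the PK plots are made only if deemed necessary (SAP 2.4.6), and population PK is reported separately. This also stands.

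Four stronger readings are tempting but not supported:

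- **The previous q2w injection is placebo.** This is an inference from labels; neither document states the order.
- **A 30-day interruption leaves 17–29% of the trough in either arm.** A reader might infer this from Protocol 10.3.1 ("A discontinuation of IMP that is greater than 30 days will be considered permanent"). In the model it needs a last active dose 35 days (qw) or 42 days (q2w) before the sample, and the protocol does not say how the 30 days are counted. A 28-day dose-to-dose gap gives 27–40% in qw and 41–53% in q2w.
- **The two-hour limit is at fault.** Two hours of decay changes the concentration by 1 − exp(−ke/12), or 0.4–0.5%. The limit does no harm.
- **The plan will produce a false exposure-response finding.** No such analysis is firmly specified, and the missed-dose rate is unknown.

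**Conclusion.** The point holds as a gap in SAP definitions. As written, a pre-dose sample after a missed active dose counts as C_trough and is averaged into C_trough,av,ss. In the alternating q2w arm, the one dosing-related check can be met by a placebo injection. Protocol 9.3.1.1 is not itself in error.

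Per affected sample the error is large: about 41–53% of the scheduled trough remains in q2w and 65–75% in qw. Per affected patient it is moderate: C_trough,av,ss is lower by about 12–15% or 6–9% if one of four troughs is affected. Per arm it cannot be stated without a missed-dose rate.

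These figures rest on the one-compartment linear model, and the q2w figures also on active drug being given in even weeks. Protocol 4.1 reports less than dose-proportional exposure, so the linear model is an approximation. If placebo came first, the q2w samples would not be troughs at all, so the definition needs the last active injection under either order. The primary efficacy test is not affected. The change is worth making because it is cheap and serves a secondary objective.

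**What to change.** In SAP 2.1.5, Table 8 and the sentence under Table 7:

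- Refer to the previous active injection wherever the text now refers to the previous injection.
- Count a pre-dose sample as C_trough, and include it in C_trough,av,ss, only if the last scheduled active injection (one week earlier in qw, two weeks earlier in q2w) was given within its dosing window.
- List the remaining samples separately with time since last active injection, and keep them available for exposure-response and population PK work.
- State the order of active and placebo injections used in the q2w arm.
- Reconcile Week 4, which is a trough time in 2.1.5 but missing from Table 8.

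The two-hour limit can stay.

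The cost is some SAP wording and one derivation from administration dates and kit numbers, which are already recorded (Protocol 8.7.1, SAP 2.5.1). The downside is somewhat fewer samples in the trough summary.

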9.3.1.2 Pharmacokinetics handling procedure

Detailed procedure of sample preparation, storage and shipment are described in the specific laboratory manual. Five (5) ml blood volume is to be collected for each PK and ADA sample.

Table 1 – Plasma samples handling for PK (SAR156597) and immunogenicity (anti-SAR156597)

Sample type	SAR156597	anti-SAR156597
Matrix	Plasma	Plasma
Blood sample volume	3mL (3 aliquots)	2mL (2 aliquots)
Anticoagulant	CPD (Citrate Dextrose Phosphate)	
Storage conditions	≤-20°C	

9.3.1.3 *Bioanalytical method*

9.3.1.3.1 *SAR156597 assay*

All plasma samples to be tested for SAR156597 samples will be analyzed by Bertin pharma (Saclay, France).

A validated ELISA is used for the quantification of SAR156597 in human plasma. Biotinylated IL-4 coated on a streptavidin plate is used to capture SAR156597, which is then detected by SulfoTag-IL-13. This format, which uses electrochemiluminescence detection, is able to detect SAR156597 with an LLOQ of 0.05µg/mL.

9.3.1.3.2 *Anti-drug antibodies*

All anti-SAR156597 antibody samples will be analyzed by the Bioanalysis and Biomarkers domain in DSAR OC Montpellier (France).

For the analysis of potential anti-SAR156597 antibodies (ADA) in human plasma, a validated bridging qualitative ELISA using electrochemiluminescence detection will be used.

Positive samples in screening assay will then be tested in a confirmatory assay (competition with SAR156597) in order to demonstrate the presence of antibodies and eliminate false positive results generated from the initial screening assay.

Interference of SAR156597 in the ADA assay will be documented so that the highest drug concentration that does not affect the limit of ADA detection is known and the interpretation of immunogenicity takes into account this parameter.

Additional information on the bioanalytical method for anti-SAR156597 antibodies will be provided in the Laboratory Manual.

Samples that are ADA positive will be further evaluated for their potential neutralizing activity with an assay currently in development.

In the interim, the sponsor will store frozen specific aliquots for neutralizing activity testing if necessary.

9.3.1.3.3 *Half-arm exchange molecule assessment*

If necessary, half-arm exchange of SAR156597 with endogenous hIgG4 may be assessed on specific PK sample aliquots.

9.3.1.4 *Pharmacokinetics parameters*

SAR156597 concentrations at selected timepoints after the last dose will be reported using descriptive statistics.

Additional PK parameters will be estimated using the population PK approach such as C_{max}, t_{max} and AUC at steady state.

PoP PK analysis will be presented in a separated stand alone report.

